10.1 Adverse Events

The incidence of treatment-emergent AEs (TEAE) will be summarized and tabulated by treatment group, MedDRA (Version 24.0 or higher) System Organ Class (SOC) and Preferred Term (PT). A TEAE is defined as an AE that first occurred or worsened in severity after the first administration of study treatment.

AEs that cannot be definitely determined as occurring prior to first study drug administration will be counted as TEAEs unless either the partial start date or a partial or complete end date indicates the AE as occurring prior to treatment. Partial dates entered in the AE form will be imputed for the purposes of determining whether the record is a treatment emergent adverse event based on the following:

- AE onset dates with missing day and non-missing month will be assumed to occur on the first day of the non-missing month, except for AEs occurring in the month and year of first dosing of study drug, in which case the date will be imputed using the date of first dosing of study drug.
- AE onset dates with missing day and month will be assumed to occur on the first day
 of the non-missing year (i.e., January 1), except for AEs occurring in the year of first
 dosing of the study drug, in which case the date will be imputed using the date of the
 first dosing of study drug.
- Partial or missing AE resolution dates will not be imputed.

Several occurrences of the same AE in one subject will be counted once at the worst severity grade. If severity is missing, the event will be classified as of unknown severity for analysis and summarization.

The relationship of each AE to the study drug will be grouped as related (definitely, probably, possibly related) or unrelated (unlikely to be related, unrelated). Several occurrences of the same AE in one subject will be counted once and the one with the closest relationship to study medication will be counted. If an AE is missing the relationship to study medication, the event will be assumed to be related to study drug for analysis and summarization.

AEs will be further categorized by Study Part (1, 2, 3) as follows:

- Part 1 (Day 1 to Week 28): includes all AEs that first occurred or worsened in severity after the first study medication administration, but do not start after the Week 28 study medication administration.
- Part 2 and 3 (Week 28 and beyond): includes all AEs that first occurred or worsened in severity after the Week 28 injection. These will be performed for the final analyses.

| Effective Date: 10-AUG-2020 | Page 41 of 61 |
|-----------------------------|---------------|

Non-TEAEs will be listed only and will not be included for analysis and summarization.

All AEs will be presented in a by-treatment and by-subject listing for Part 1, detailing the verbatim term, SOC, PT, injection site reaction or not, related to study indication or not, start date, stop date, time since most recent dose of IP, severity, outcome, relationship to study drug, action taken regarding study drug, other action taken, seriousness and criteria for seriousness. Serious AEs (SAEs) and TEAEs leading to study medication discontinuation, AEs of Special Interest (AESI), and events of clinical interest (ECI) will also be presented in separate listings.

An AE profile for the SAF will be provided for Part 1, Parts 2 and 3, and overall, which summarizes the subject incidence, by treatment received for the following information:

- Any TEAEs;
- Drug-related TEAEs;
- Any TEAEs with an outcome of death;
- Treatment-emergent SAEs;
- Drug-related treatment-emergent SAEs;
- TEAEs leading to discontinuation of study medication;
- Drug-related TEAEs leading to discontinuation of study medication;
- Any AEs of special interest, including:
 - Injection site reactions
 - Severe infections
 - o Malignancies (excluding carcinoma in situ of the cervix).
 - Non-melanoma skin cancer
 - Melanoma skin cancer
 - Major Adverse Cardiovascular Events (MACE)
 - Study treatment-related hypersensitivity reactions (e.g., anaphylaxis, urticaria, angioedema, etc.).

| Effective Date: 10-AUG-2020 | Page 42 of 61 |
|-----------------------------|---------------|

Study treatment-related hypersensitivity reactions will be identified based on Sponsor review of treatment-blinded listings of AE preferred terms prior to declaration of the IA DB freeze.

The number and percentage of subjects with TEAEs will be summarized for each treatment arm and/or in total by SOC and PT. Drug-related TEAEs, TEAEs leading to discontinuation of study drug, drug-related TEAEs leading to discontinuation of study drug, treatment-emergent SAEs, and drug-related treatment-emergent SAEs, AESI and ECI will be summarized in the same manner. For these summaries, subjects with multiple AEs will be counted only once per SOC and PT.

TEAEs by maximum severity and TEAEs by relationship to study treatment, and commonly occurring TEAEs, i.e., those that occur in 1% or more of the subjects in either treatment arm, will be summarized by SOC and PT by treatment received in Part 1, Parts 2 and 3, and overall.

Injection site reactions will be described in a by-subject listing and may be summarized separately if deemed necessary.

COVID-19 related adverse events may also be summarized separately if deemed necessary.

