9.5 Interim Analyses (IA)

An interim analysis may be performed. An external program-independent Data Monitoring Committee (DMC) may be established to conduct this unblinded interim analysis, review the unblinded results and make recommendations regarding the continuation of the study. To maintain the scientific reliability of possible final results and guard from introducing any potential bias into the conduct of the study and analysis, individuals involved in the interim analysis will not be involved in any operational aspect of the study. Further details of the unblinded interim analysis, in particular, its scope, the processes put in place to maintain study integrity, team structures, and responsibilities, will be documented in the Data Monitoring Committee Charter and/or a separate document. The interim analysis could include an unblinded sample size re-estimation (SSRE). The sample size of the study could be increased as a result of this SSRE. In the event of an increase in sample size, the total sample size of the study will not exceed a total of approximately 282 randomized subjects.

Following the last subject's Week 28 visit (or early termination prior to Week 28), a primary analysis may be conducted on available data to evaluate safety and efficacy and develop a clinical study report based on the data evaluated up to Week 28 visit. This analysis will be performed by the CRO; the Sponsor, and the DMC may not be involved in this analysis.

In the event of such an analysis, subjects who complete Part 1, all assessments of efficacy and safety before or on the date of injection at Week 28 (or Day 210 for subjects who do not have Week 28 injection), will be fully evaluated. Study centers, subjects, and study team members directly involved in study activities will remain blinded to study treatment assignments until the last subject completes their active treatment period (Week 52) and wash-out period. A separate document will provide further details related to the unblinding of personnel involved in reporting activities for the IAs. Sharing of subject-level unblinded information for the IAs will be confined to a designated unblinded study team.

The SAP will describe the planned IAs in greater detail.

9.6 **Monitoring Committee**

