The term significant disability refers to any condition that impairs physical/physiological well-being to the extent that the subject is unable to function normally. Physical disability may include, but is not limited to, permanent disability of locomotion or motility, but also systemic permanent dysfunction including heart failure, liver insufficiency or pulmonary fibrosis.

e) Is a congenital anomaly/birth defect

f) Is an important medical event:

Important medical events that may not result in death, be life-threatening or require hospitalization may be considered as an SAE when, based on appropriate medical judgment, they may jeopardize the subject, or the subject may require medical or surgical intervention to prevent one of the outcomes listed in this definition.

Recording and Follow-up of AE and/or SAE Definition of the Adverse Event Reporting Period

The AE/SAE reporting period for safety surveillance begins after subject signs ICF. The safety surveillance continues until 20 weeks from last dos

e of study treatment administration. Any AE/SAE occurred post 20 weeks from last dose of study treatment administration will be reported if it is considered related to study treatment by the Investigator.

Unexpected Adverse Event

Any adverse event that is not identified in nature, severity, frequency, or outcome in Investigator Brochure (IB) will be considered as unexpected. Most recent version of IB will serve as reference safety information for assessment of expectedness of SAEs.

AE and SAE Recording

- When an AE/SAE occurs, it is the responsibility of the Investigator to review all documentation (e.g. hospital progress notes, laboratory reports, and diagnostics reports) related to the event.
- The Investigator will then record all relevant AE/SAE information in the eCRF. Each event must be recorded separately.
- It is not acceptable for the Investigator to send photocopies of the subject's medical records to IQVIA Clinical Pharmacovigilance and Safety Services in lieu of completion of the AE/SAE eCRF page.
- There may be instances when copies of medical records for certain cases are requested by IQVIA Clinical Pharmacovigilance and Safety Services. In this case, all subject identifiers, with the exception of the subject number, will be redacted on the copies of the medical records before submission to IQVIA Clinical Pharmacovigilance and Safety Services.

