Following the last subject's Week 28 visit (or early termination prior to Week 28), Week 28 analysis may be conducted on available data to evaluate safety and efficacy, and a Week-28 clinical study report (CSR) may be developed after database lock (DBL). In this case, when all the randomized patients have either completed the Week 28 evaluations or have stopped study participation prior to the Week 28 visit, the first database freeze (DBF) will occur (referred to as Week 28 DBF hereafter). When all patients randomized in this trial have either completed the Week 72 evaluations or have ceased study participation prior to the Week 72 visit, the second DBL will take place [referred to as the Final (Week 72) DBL henceforth], and subsequent CSR will be generated. The sponsor might opt to have a single DBL and CSR at the last subject's Week 72 visit (or early termination prior to Week 72) without a DBL at Week 28.

All assessments in PART 1 are scheduled to happen before or on the date of injection at Week 28. The analysis of efficacy and safety endpoints for PART 1 will follow the analysis visit window and definitions as specified in the sections below.

PART 2: Double-blind Active Treatment Extension (Week 28 to Week 52)

At Week 28, subjects initially randomized to placebo will be switched over to receive tildrakizumab 100 mg at Weeks 28, 32, and 44. Subjects initially randomized to tildrakizumab 100 mg will continue to receive tildrakizumab at Weeks 28, 40, and 52. In order to maintain the blind, subjects in both treatment arms will receive matching placebo injections at specified time points as described in the Schedule of Activities (SoA) in the Clinical Protocol.

Subjects who experience significant worsening of plaque psoriasis at Week 28 (defined as an increase in s-PGA by, at least, 2 from the baseline measurement) will be discontinued from treatment. Subjects who do not fulfill this criterion at Week 28 will continue to receive tildrakizumab in Part 2 as described above.

All assessments in PART 2 are scheduled to happen after the date of injection at Week 28 and before or on the date of injection at Week 52. The analysis of efficacy and safety endpoints for PART 2 will follow the analysis visit window and definitions as specified in the sections below.

PART 3: Observational Safety Follow-up (Week 52 to Week 72)

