3.3 Analysis Time points

Unless specified otherwise, efficacy and safety endpoints will be analyzed according to their scheduled study visits; unscheduled and early termination visits will be mapped to windowed analysis visits defined by actual study day as in table 1.1 below. If there is no evaluation available from the scheduled study visit, and more than one non-missing evaluation is assigned to an analysis window, the evaluation closest to the target day will be used for the analysis. If the two visits are equidistant from the target day, the earlier visit will be used. For early terminated patients, Part 3 is to start the day of last assessment after the last injection plus 28 days.

The following analysis visit windows will apply:

Table 1.1 Analysis Visit Windows

For: ViSENPsO, NAPSI, mNAPSI, PGA-S, BSA, PASI, and C-SSRS

| Derived Visit | Week | Target Day | Analysis Window |
|---|------|------------|-----------------|
| Part 1: Double-blind Placebo-controlled | | | |

| Effective Date: 10-AUG-2020 | Page 17 of 61 |
|-----------------------------|---------------|

| | _ |
|--|---|
| | |

| _ | |
|-----------------------------|---------------|
| Effective Date: 10-AUG-2020 | Page 18 of 61 |

In particular, NRS pain score will be recorded daily in patient diary for the 7 days leading up to each scheduled visit. The analysis visit for NRS will be assigned the same as for the subsequent visit according to Table 1.1, ie, as 7 consecutive days prior to that visit. In the event of a missed visit, the available NRS scores will be mapped to an analysis visit according to Table 1.1, using the last diary entry date as anchor. Any NRS entries outside of the 7-day window will be excluded from the calculation of average NRS. At least 4 out of the 7 daily records are required to calculation of average.

All other assessments (ECG, laboratory data) will be analyzed according to the assigned (nominal) visit unless otherwise specified.

[figure not shown]
For any events/assessments on or after the first administration of study drug, study day is calculated as: event/assessment date – date of first administration of study drug + 1. As such, Day 1 is defined as the date of first administration of study drug.

For any events/assessments before the first administration date, study day is calculated as event/assessment date – date of first administration of study drug.

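### Does tying the end of Part 1 to the Week 28 dose distort the adverse event tables for subjects who never receive that dose?

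*SAP*

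**What the plan says.** SAP 10.1 divides adverse events by study part. The Part 1 rule opens "Part 1 (Day 1 to Week 28): includes all AEs that first occurred" and closes with the condition "but do not start after the Week 28 study medication administration". The rule for Parts 2 and 3 carries a label meaning Week 28 onward and "includes all AEs that first occurred or worsened in severity after the Week 28 injection". SAP 7.3 splits concomitant medications at Week 28 dosing in the same way.

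Three other places bear on the boundary:

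- SAP 2.1 says: "The analysis of efficacy and safety endpoints for PART 1 will follow the analysis visit window and definitions as specified in the sections below".
- SAP 3.3, on visit mapping, says: "For early terminated patients, Part 3 is to start the day of last assessment after the last injection plus 28 days".
- Protocol 9.5, on the optional analysis after the last Week 28 visit, begins "In the event of such an analysis, subjects who complete Part 1" and limits the data to assessments up to the Week 28 injection, "or Day 210 for subjects who do not have Week 28 injection), will be fully evaluated".

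On the length of follow-up, Appendix 3 of the Protocol (adverse event reporting period) says: "The safety surveillance continues until 20 weeks from last" dose.

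**The concern.** The plan expects some subjects to be followed without a Week 28 injection. Early escape at Week 16, discontinuation at Week 28 for worsening and voluntary stopping all lead into safety follow-up. For these subjects the Part 1 condition is always met and the condition for Parts 2 and 3 never is. An event at Week 33 would then sit under a Part 1 heading that names Week 28 as its end.

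Part 1 is the only randomised, placebo-controlled safety comparison. If off-treatment events from after Week 28 enter its incidence tables, or if programmers choose different boundaries, the comparison is less clean than its title suggests. SAP 3.3 seems to add a further boundary, about four weeks after the last injection.

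**Working it through.** **Timeline.** Use day = 7 × week + 1. Part 1 doses are at Weeks 0, 4 and 16 (Protocol 6.0), and surveillance runs 20 weeks from the last dose (Protocol Appendix 3).

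| Last dose | End of surveillance | Weeks past Week 28 |
|---|---|---|
| Week 0 | Week 20 (Day 141) | 0 |
| Week 4 | Week 24 (Day 169) | 0 |
| Week 16 | Week 36 (Day 253) | 8 |

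Week 28 is Day 197, so Day 210 lies 13 days after it. Apart from late events judged related to treatment, only a last dose at Week 16 takes the literal rule past the label.

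**Who is affected.** Entry requires an s-PGA of at least 3 (Protocol 5.1) on a 0 to 5 scale (Protocol Appendix 20). A 2-point rise is therefore possible only from 3 to 5, and the worsening route is narrow. The number of affected subjects is not given. As an illustrative upper value, take the whole 10% dropout allowance: 0.10 × 48 = 4.8, about 5 per arm.

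**Does SAP 3.3 conflict?** A last dose at Week 16 (Day 113) plus 28 days gives Day 141, and 253 − 141 = 112 days, which looks like a large disagreement. But the SAP 3.3 paragraph maps visits, yields to anything specified elsewhere, and leads to a window table headed for efficacy scales and the C-SSRS. Adverse events and medications have their own rules in 10.1 and 7.3, and those govern. Day 253 is simply where data collection ends. The 112 days are not a spread between competing adverse event rules.

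**Exposure.** Person-weeks per arm in Part 1: 48 × 28 = 1,344. One affected subject adds 8/1,344 = 0.6%; five add 40/1,344 = 3.0%.

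**Subject incidence (the planned output).** Assume a constant hazard and a 28-week incidence p of 10% to 50%; neither figure is in the documents. The expected rise per affected subject is 1 − (1 − p)^(T/28) − p, where T is the week at which counting stops. Multiply by 1/48 or 5/48 for the arm.

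| Counting stops | Rise per subject, p = 10% / 50% (points) | Arm shift, 1 subject (points) | Arm shift, 5 subjects (points) |
|---|---|---|---|
| Day 210 (T = 29.86) | 0.63 / 2.25 | 0.01 to 0.05 | 0.07 to 0.23 |
| Week 36 (T = 36) | 2.67 / 8.98 | 0.06 to 0.19 | 0.28 to 0.94 |
| Week 40 (T = 40) | 3.97 / 12.85 | 0.08 to 0.27 | 0.41 to 1.34 |

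The Week 40 row applies if follow-up is counted from the end-of-treatment visit, as Protocol 8.3.1 words it: 16 + 4 + 20 = 40.

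**Yardstick.** The standard error of one arm's proportion with 48 subjects is √(0.10 × 0.90/48) = 4.3 points at 10% and √(0.50 × 0.50/48) = 7.2 points at 50%. Even the largest shift in the table is well below that.

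**The case for a change.** The strongest case for a change has four parts.

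- **Database timing does not remove the problem.** SAP 2.1 allows a single lock at Week 72, and even a Week 28 freeze waits for the last subject, so earlier subjects' late follow-up is already recorded. This stands.
- **Expected shifts hide single events.** One reassigned event that is a subject's only event of its type moves arm incidence by 1/48 = 2.1 points, which matters to the eye for sparse categories such as MACE or malignancy. The arithmetic stands. Events that rare are read case by case, however, and the Part 1 listing gives time since the most recent dose. The same 2.1 points exceeds the 1% threshold for common events wherever the event falls, so that threshold does not discriminate here.
- **Denominators.** SAP 10 uses the whole safety set, so a subject without the Week 28 dose stays in the denominator for Parts 2 and 3 but cannot contribute an event. This is true as written. A new cut-off would largely leave it in place, because subjects last dosed at Week 0 or 4 have finished surveillance before Week 28 anyway.
- **A cross-reference to Day 210 is cheap.** It is, and it would tidy the text. It would not clearly improve the analysis: off-treatment events up to 13 days past Week 28 would stay in Part 1, and later ones would be reported apart. Choosing between that and counting to the end of surveillance is a matter of preference.

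The dose boundary also has a rationale. It marks when placebo subjects switch to active drug, and a placebo subject who misses the Week 28 dose never switched. Keeping that subject's events in Part 1 avoids putting unexposed time into the active-treatment period.

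**Conclusion.** No change is needed. The visible SAP 10.1 and 7.3 lack an explicit clause for subjects without a Week 28 injection, and the literal reading does not match the section's own labels. This is a gap that analysts can fill sensibly. The literal rule is deterministic and defensible, and Protocol 9.5 supplies Day 210 for the Week 28 analysis. No conflict with SAP 3.3 remains once the specific rules are given precedence.

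The expected effect is 0.06 to 0.94 percentage points on arm-level incidence with surveillance to Week 36, or up to 1.34 points if follow-up runs to Week 40. It is confined to descriptive by-part tables of adverse events, with the same reassignment in the medication tables. The overall adverse event profile, the efficacy endpoints and every hypothesis test are untouched.

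These figures assume a constant hazard, a 28-week incidence of 10% to 50%, and one to five affected subjects per arm. Five is generous: all of them would have to be last dosed at Week 16 and remain in follow-up, whereas a subject who withdraws consent completely contributes none. The body of the visit-window table and several SAP sections are not visible, and a rule for these subjects may already be there.

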Up to approximately 35 Investigators and study centers globally, are expected to participate in this study.

Number of Subjects:

Approximately 96 eligible subjects will be randomly assigned to study treatment for an estimated total of 48 subjects per treatment arm. It is assumed up to 10% of the subjects may drop out, leaving 43 evaluable subjects per arm for the primary endpoint analysis at Week 28.

Treatment Groups and Duration:

The study duration per subject will be approximately 18 to 19 months, and the total duration of the study will be approximately 3 years.

The study consists of a screening period of 28 days, a 52-week treatment period (a 28-week double-blind placebo-controlled treatment period followed by a 24-week double-blind, active treatment period), and a 20-week observational follow-up period.

Part 1: Double-blind, placebo-controlled part, where subjects will receive either tildrakizumab 100 mg (Arm A) or placebo (Arm B) SC at Weeks 0, 4, and 16. At Week 16, subjects who experience significant worsening of plaque psoriasis (defined as an increase in s-PGA by at least 2 from the baseline measurement) will be eligible for an early escape. Subjects selected for early escape by the Principal Investigator at Week 16 will have study medication discontinued and will complete the End of Treatment visit assessment, followed by the observational safety follow-up period.

Part 2: At Week 28, subjects initially randomized to placebo will be switched over to receive tildrakizumab 100 mg at Weeks 28, 32, and 44. Subjects initially randomized to tildrakizumab 100 mg will continue to receive the active drug at Weeks 28, 40, and 52. In order to maintain the blind, subjects in both treatment arms will receive matching placebo injections at specified time

points as described in the SoA. Subjects who experience significant worsening of plaque psoriasis at Week 28 (defined as an increase in s-PGA by, at least 2 from the baseline measurement) will be discontinued from treatment.

Part 3: After Week 52 (or early termination of study treatment prior to Week 52), subjects will enter the 20-week observational safety follow-up period when tildrakizumab treatment will be stopped.

Statistical methods:

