1.3 Schedule of Activities

Table 1: Schedule of Activities

	Screening		1		PART 3											
		Double-blind Placebo-controlled									Double-blind Active Treatment					
Week		0	4	8	12	16a	20	24	28 ^b	32	36	40	44	52°	72	
		(Baseline)												EoT	EoS	
Visit Number	1	2	3	4	5	6	7	8	9	10	11	12	13	14	15	
Day	Within 28	1	+/-	+/-	+/-	+/-	+/-	+/-	+/-	+/-	+/-	+/-	+/-	+/-	+/-	
	Days		3 days	3 days	7 days	7 days	7 days	7 days	7 days							
Written informed consent	X															
Inclusion/Exclusion criteria	X	X ^d														
Demographic information	X	Xe														
Physical examination	X	X												X	X	
Vital signs	X	X	X	X	X	X	X	X	X	X	X	X	X	X	X	
AEf/Concomitant medications	X	X	X	X	X	X	X	X	X	X	X	X	X	X	X	
Medical/ Medication history	X															
Chest X-ray ^g	X															
QuantiFERON ^h	X															
HIV, HbsAg, and HCV serology	X															
ECG		X												X		
Randomization ⁱ		X														
IWRS entry	X	X	X			X			X	X		X	X	X	X	
Study treatment administration ^j		X	X			X			X	X		X	X	X		
Hematology/chemistry/Urinalysisk	X ^l	X							X					X	X	
Lipids ^k		X							X					X		
Serum pregnancy test	X													X		
Urine pregnancy test ^m		X	X	X	X	X	X	X	X	X	X	X	X	X		
C-SSRS ⁿ	X	X	X	X	X	X	X	X	X	X	X	X	X	X		
Efficacy assessments	X	X	X	X	X	X	X	X	X	X	X	X	X	X		
(ViSENPsO, NAPSI, mNAPSI,																
PGA-S, pain NRS, BSA, and																
PASI) ^{o, p}																
s-PGA ^q	X	X				X			X							
CGIS	X	X			X				X		X			X		

	Screening	PART 1 Double-blind Placebo-controlled							Dou	PART 3 OSFU					
Week		0 (Baseline)	4	8	12	16ª	20	24	28 ^b	32	36	40	44	52° EoT	72 EoS
Visit Number	1	2	3	4	5	6	7	8	9	10	11	12	13	14	15
Day	Within 28	1	+/-	+/-	+/-	+/-	+/-	+/-	+/-	+/-	+/-	+/-	+/-	+/-	+/-
	Days		3 days	3 days	7 days	7 days	7 days	7 days	7 days						
CGIC					X				X		X			X	
DLQI and NAPPA-QoL		X			X				X		X			X	
PGIS	X	X			X				X		X			X	
PGIS-P	X	X			X				X		X			X	
PGIC					X				X		X			X	
PGIC-P					X				X		X			X	

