8.3.2 Method of Detecting AEs and SAEs

Care will be taken not to introduce bias when detecting AEs and/or SAEs. Open-ended and non-leading verbal questioning of the subject is the preferred method to inquire about AE occurrences.

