9.2.3 Analysis of Secondary Efficacy Endpoints

Binary endpoints

The following binary endpoints will be analyzed in a similar manner as the primary efficacy endpoint based on the analysis population specified in Table 5 in Section 9. A CMH test (rather than M-N methodology) will be used, stratified by prior use of TNF-alpha inhibitors (yes or no) and baseline body weight class (≤90 kg or >90 kg).

- ViSENPsO response at Week 28 (key secondary endpoint)
- ≥ 3-point decrease in Nail Pain NRS score from Baseline at Week 28 in subjects with baseline nail pain NRS score of ≥ 3
- mNAPSI90 at Week 28
- mNAPSI100 at Week 28
- NAPSI75 at Week 28
- NAPSI90 at Week 28
- NAPSI100 at Week 28
- PASI 75 at Week 28
- PASI 90 at Week 28
- PASI 100 at Week 28
- PGA-S response at Week 28

| Effe | ective Date: 10-AUG-2020 | Page | e 35 of 61 |
|------|--------------------------|------|------------|

• 30% decrease in Nail Pain NRS score from Baseline at Week 28 in subjects with baseline nail pain NRS score of ≥3

Continuous endpoints

Change from baseline to week 28 in total-fingernail mNAPSI and total-fingernail NAPSI scores (endpoints included in the hierarchical order of Section 4.5) during the double-blinded period will be analyzed based on the ITT population using MI to handle missing data.

MI procedures for continuous efficacy endpoint (total-fingernail mNAPSI and total-fingernail NAPSI scores):

Missing post-baseline total-fingernail mNAPSI or NAPSI scores through Week 28 will be imputed for the ITT separately for each treatment group using the Markov Chain Monte Carlo (MCMC) method. 50 copies of the dataset with monotonic missing pattern will be generated. For each of the 50 datasets, missing values at scheduled visits (Weeks 4, 8, 12, 16, 20, 24, and 28) will be imputed using a monotone regression model including treatment, presence of TNF-alpha inhibitors at baseline (yes or no), baseline body weight class (≤90 kg or >90 kg), baseline mNAPSI or NAPSI score, and mNAPSI or NAPSI scores at the previous scheduled visits. Change from baseline in mNAPSI or NAPSI score will be derived based on the imputed datasets.

Once imputations are made, the week 28 data of each of the 50 complete datasets will be

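### SAP 10.1 pools Part 2 with the single-visit Part 3 in one AE column, so that column cannot be read against Part 1 and no AE column ends at Week 52

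*SAP*

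**What the plan says.** The lead-in in SAP 10.1 names three study parts as AE categories. Two bins follow: Part 1, and "Part 2 and 3 (Week 28 and beyond): includes all AEs that first occurred or worsened in severity after the Week 28 injection". The display matches the bins: "An AE profile for the SAF will be provided for Part 1, Parts 2 and 3, and overall, which summarizes the subject incidence". The tables by maximum severity, by relationship and of common events use the same three columns. The measure is the number and percentage of subjects. A subject with repeat events counts a single time within each system organ class and preferred term. SAP 10.1 contains no person-time rate.

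The Protocol Synopsis gives the part lengths: "a 28-week double-blind placebo-controlled treatment period followed by a 24-week double-blind, active treatment period), and a 20-week observational follow-up period". The Schedule of Activities has a row "AEf/Concomitant medications" marked at every visit. After Week 28 the visit weeks run "32 36 40 44 52° 72", and Week 72 is the only one in Part 3. On detection, Protocol 8.3.2 states: "Open-ended and non-leading verbal questioning of the subject is the preferred method to inquire about AE occurrences". The safety objective (SAP 2.2.4) is set over 52 weeks.

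**The concern.** Two columns that stand side by side invite comparison. Here they differ in three ways unrelated to any change in risk: length of window, spacing of visits, and whether dosing is going on. If AEs are found mainly by asking at visits, mild events in a 20-week gap are the ones most likely to go unrecorded. Arm A's Week 52 active dose falls at the start of that gap, whereas each of its other five active doses is followed by a visit 4 weeks later.

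The columns planned cover Weeks 0 to 28, 28 to 72 and 0 to 72. A reader who wants the AE experience of Part 2 dosing, or anything that stops at Week 52, cannot recover it from these tables. What is at stake is the reading of descriptive safety tables. The efficacy conclusions are not touched.

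**Working it through.** **Step 1: part lengths.** From the Schedule weeks: 28 − 0 = 28, 52 − 28 = 24 and 72 − 52 = 20, as in the Synopsis. Parts 2 and 3 together: 24 + 20 = 44 weeks.

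**Step 2: visit spacing.** The Part 1 visits are listed in SAP 9.2.3 ("missing values at scheduled visits (Weeks 4, 8, 12, 16, 20, 24, and 28") and agree with the Schedule.

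| Period | Weeks | Visits | Gaps (weeks) | Mean gap (weeks) |
|---|---|---|---|---|
| Part 1 | 28 | 7 | seven of 4 | 4.0 |
| Part 2 | 24 | 5 | 4, 4, 4, 4, 8 | 4.8 |
| Part 3 | 20 | 1 | 20 | 20 |
| Parts 2 and 3 | 44 | 6 | as above | 7.3 |

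Of the pooled time, 20/44 = 45% lies in a single gap.

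**Step 3: effect of length alone.** With constant hazard and full capture, a proportion p over 28 weeks becomes 1 − (1 − p)^(44/28) over 44 weeks. So 5% becomes 7.7%, 10% becomes 15.3% and 40% becomes 55.2%. The planned percentages rise.

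**Step 4: effect of visit spacing alone.** Neither document gives a rate of recall loss, so this is an assumption shown over a range. If events are forgotten at a continuous rate r per week until the next visit, the share captured over a gap of G weeks is (1 − exp(−rG))/(rG). Each period averages its gaps, weighted by length.

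| r | Part 1 | Part 2 | Part 3 | Parts 2 and 3 | Pooled ÷ Part 1 | Part 2 ÷ Part 1 |
|---|---|---|---|---|---|---|
| 0.02 | 0.96 | 0.95 | 0.82 | 0.89 | 0.93 | 0.99 |
| 0.05 | 0.91 | 0.88 | 0.63 | 0.77 | 0.85 | 0.97 |
| 0.10 | 0.82 | 0.78 | 0.43 | 0.62 | 0.75 | 0.95 |

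Ratios are taken before rounding. With faster forgetting, a recall half-life of 4 weeks, the pooled ratio is 0.68 and the Part 2 ratio 0.92. With no forgetting, both are 1.00.

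**Step 5: both effects together.** For 10% in Part 1, the pooled column shows 1 − 0.90^((44/28) × ratio). With ratios 0.93, 0.85 and 0.75 this is about 14.3%, 13.1% and 11.7%. The column would fall below Part 1 only if the pooled ratio were under 28/44 = 0.64, which in this model needs a recall half-life below about 2.9 weeks.

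**Step 6: after splitting.** Part 2 alone captures 0.95 to 0.99 of Part 1 per person-time over the range in Step 4, so most of the ascertainment difference goes. A length difference of 24 against 28 weeks remains: 10% in Part 1 corresponds to 1 − 0.90^(24/28) = 8.6% in Part 2.

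**The case against.** The strongest reply is that this is a matter of presentation. Safety analysis is descriptive and no test of one period against another is planned. Both arms share one visit schedule, so comparison between arms within a period is sound. AEs are also recorded at unscheduled visits (Protocol 8.0). SAEs go to the CRO within 24 hours, and AESIs, which include injection site reactions, are reported as if they were SAEs (8.3.6). The Week 52 dose is given at the study center, where an immediate reaction can be seen. The protocol justifies the 20-week follow-up by the drug's long half-life, which is a reason to keep those weeks in view.

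Most of this stands, and it limits the point to reading across periods and mainly to non-serious events. Two things remain. The reporting clock starts when the investigator becomes aware, and awareness of a mild event after Week 52 may wait until Week 72. The half-life argument supports collecting AEs in Part 3 but does not require merging them with the dosing period.

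A reader might also infer that recorded AE rates must fall with longer time on drug, even per person-year. The documents do not support that. The planned measure is a subject percentage, and at constant hazard it rises under every loss rate in Step 4. No person-year rate appears in SAP 10.1. A fall per person-time depends wholly on assumed recall loss. Nor do the columns track time on drug: Arm B starts active drug only at Week 28, and Part 3 has no dosing.

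**Conclusion.** The point holds as one of comparability. The pooled column differs from Part 1 in length (44 against 28 weeks) and in visit density (mean gap 7.3 against 4.0 weeks). These push in opposite directions, so a rise or a fall between the columns has no clear meaning. Separately, no AE column isolates Part 2 dosing or ends at Week 52, and the three-part lead-in in SAP 10.1 disagrees with its two bins.

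The visit counts and part lengths come from the documents. The capture ratios rest on the assumed loss rates and count scheduled visits only, so unscheduled contacts would shrink the effect. SAEs depend less on visit spacing. The SAP's exposure section and table list are not in the text available, so a person-time table planned there cannot be ruled out; it would deal with length but not with how often subjects were asked. This is a cheap improvement to the safety tables and does not make the safety plan unsound.

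**What to change.** In SAP 10.1, for subjects who received the Week 28 injection, replace the pooled bin with two:

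- **Part 2:** onset or worsening after the Week 28 injection, up to and including the Week 52 injection date (the cut in SAP 2.1). For those who stop early in Part 2, the end is the Part 3 start day in SAP 3.3.
- **Part 3:** everything later, labelled as a follow-up with a single scheduled visit.

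Leave the Part 1 bin as it is. Applying the SAP 3.3 start day to subjects who stop before Week 28 would move their later AEs out of the placebo-controlled column, so the text should say that the rule does not apply to them. Keep the overall column. Where Part 2 is read against Part 1, state the 24- and 28-week lengths in the table.

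The cost is one more column in the AE tables and smaller counts in each of Part 2 and Part 3. No new data are needed.
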